14.1. Secondary endpoints

Each secondary cognitive endpoint will be analysed using the same primary endpoint progression model and a traditional mixed model for repeated measures (MMRM) analysis. Modifications are needed as these are not normalised by sex and age. Thus, assumptions on μ and τ should be re-considered.

 EPAD - 115736	D2.11 Master Statistical Analysis Plan for the EPAD Platform Proof-of-Concept Trial		
	WP2. Statistical/Methodology Engine Room	Version: v2.0 – Final	
	Author(s): [name], [name], [name]	Security: PU	28/36

Subset analyses and additional analyses for each intervention will be specified in the intervention specific SAP.

15. Safety

This section describes only the final analysis. For the interim analyses, only key safety analyses will be performed. If there is a major safety signal, the DSMB will recommend stopping the IST. The interim analyses are covered by the DSMB charter.

AEs will be coded using the Medical Dictionary for Regulatory Activities (MedDRA) coding dictionary. Standard summary tables and listings will be produced. All AEs with an onset between start of treatment and end of the residual effect period (REP). The REP will be defined in the ISA.

All treated patients will be included in the safety analysis. In general, safety analyses will be descriptive in nature and will be based on Sponsor standards. No hypothesis testing is planned.

Statistical analysis and reporting of AEs will concentrate on treatment-emergent AEs. To this end, all AEs occurring between start of treatment and end of the REP will be considered ‘treatment-emergent’. The REP is defined in the ISA. AEs that start before first drug intake and deteriorate under treatment will also be considered as ‘treatment-emergent’.

Frequency, severity, and causal relationship of AEs will be tabulated by system organ class and preferred term after coding according to the current version of the MedDRA.

Laboratory data will be analysed both quantitatively as well as qualitatively. The latter will be done via comparison of laboratory data to their reference ranges. Values outside the reference range as well as values defined as clinically relevant will be highlighted in the listings. Treatment groups will be compared descriptively with regard to distribution parameters as well as with regard to frequency and percentage of patients with abnormal values or clinically relevant abnormal values.

Vital signs, physical examinations, or other safety-relevant data observed at screening, baseline, during the course of the trial and at the end-of-trial evaluation will be assessed with regard to possible changes compared to findings before start of treatment.

Shift analyses from baseline to post-baseline visits.

Details of any specific safety assessments required for the trial drug will be reported in the ISA.

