4.4. Safety objectives(s)

The safety of an intervention will be monitored throughout the trial.

5. Study Design

This is a multi-centre, multi-national, double-blind, randomized, placebo-controlled, adaptive, perpetual platform clinical trial to investigate the efficacy and safety of multiple drugs simultaneously or sequentially.

There will be multiple interventions, where the research participants on an intervention and its specific blinded placebo are labelled as the intervention specific trial population. Intervention specific trial populations may start at different time points in the course of the trial. Therefore, the double-blind will be maintained within an intervention specific trial population between the different arms in that cohort. Research participants will not be blinded to which intervention specific trial they participate in. For an intervention specific trial, the number of intervention arms versus placebo will be defined in the Intervention Specific Appendix. The randomization ratio within each intervention specific trial is 3:1 (total active arms: placebo). Each intervention arm within an intervention specific trial is labelled as a subarm.

This adaptive platform design will utilise common control research participants from multiple intervention specific trials and common minimum success and futility criteria evaluated at the interim analyses. The ISA may describe further adaptive features, referring to the IST, such as changes in allocation ratios for the active arms, when there are multiple active arms

Research participants who have been enrolled in the LCS for the below minimum time points will be invited to participate in the PoC trials (note that the criteria referring to CSF may have been assessed at an earlier time point):

1. For prodromal research participants they have completed Visit 2/Month 6 procedures in the EPAD LCS.
2. For preclinical research participants they have completed Visit 3/Month 12 procedures in the EPAD LCS.

The allocation procedure is illustrated in Figure 1. Research participants who provide consent at the transition visit will have an eligibility check done and then be randomly allocated to one of the ongoing Intervention-specific Trials in the EPAD PoC trial for which they are eligible. The participant will be informed of this allocation and provided with written information specific to the IST, then subject to consent they will begin screening procedures for the IST.

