Clinically relevant abnormal findings that become apparent following baseline assessments will be reported as (S)AEs. 'Seriousness' will be defined, when required, in the Intervention Specific Appendix.

 EPAD - 115736	D2.11 Master Statistical Analysis Plan for the EPAD Platform Proof-of-Concept Trial		
	WP2. Statistical/Methodology Engine Room	Version: v2.0 – Final	
	Author(s): [name], [name], [name]	Security: PU	18/36

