7.5.7. Adverse events

This includes adverse events covering AE, SAE, AR (adverse reactions), AESI (adverse events special interest), and TLAE (adverse events that are treatment limiting or lead to early discontinuation). See Section 15 for further details on adverse events. The exact safety assessments required for a specific substudy will be outlined in the ISA.

8. Analysis set(s)

Analysis sets will be given a two or three-level name. The first level concerns whether patients were randomized, treated and whether they have valid measurements on the primary outcome (ASRS/ASTS/FAS). The second level concerns which type of control patients are included (ISA-controls/Concurrent-controls/All-controls). For the third level, a qualifier “controls-only” may be added to select only control patients. All sets refer to a single IST but this is not part of the naming. All sets are restricted to subjects within the strata (pre-clinical/pro-dromal; APOe-status) covered by the IST. Other inclusion/exclusion criteria are by default not accounted for, as they may not be assessed in all ISTs. However, an ISA-SAP may specify further restrictions.

The primary efficacy analysis is performed on the set FAS-concurrent controls, with sensitivity analysis on other analysis sets. Poolability of controls is done on the set FAS-concurrent controls-controls only. Safety analyses are done on the set ASTS-concurrent controls.

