8.2. Second level

IST controls: All subjects in all treatment arms in the IST.

Concurrent controls: All subjects in all treatment arms in the IST supplemented with control subjects from other ISTs, defined as follows: The present IST has a First Subject First Visit (FSFV) and Last Subject First Visit (LSFV), and a specified intended study duration. The dates refer to the baseline visit. The placebo subjects contributing from other ISTs are all subjects with a Visit 2 (baseline) date between the dates of the first subject first visit (FSFV) and the last subject first visit (LSFV) in the focus IST(both

 EPAD - 115736	D2.11 Master Statistical Analysis Plan for the EPAD Platform Proof-of-Concept Trial		
	WP2. Statistical/Methodology Engine Room	Version: v2.0 – Final	
	Author(s): [name], [name], [name]	Security: PU	21/36

dates included). Here FSFV and LSFV refer to the baseline visits. Only data from research participants from the strata included in the focus IST are shared. Individual data will be used until the minimum of the study durations of the relevant study and the other study. So, if the actual IST runs over 2 years and the other study over 4 years, only data up to 2 years will be shared. On the other side if the actual IST runs over 4 years and the other study over 2 years, still only data up to 2 years will be shared as further data are not available.

All controls: Defined similar to the concurrent controls, but without the condition of start in PoC between FSFV (inclusive) and LSFV (inclusive). Before unblinding, a cut-off will need to be set regarding the last enrolment day to include. The cut-off date should allow for including data from the Month 6 visit. Research participants who cannot have experienced their Month 6 visit are not included.

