Medical judgment by the PI should be used to determine any causal relationship to the AE/SAE, considering all relevant factors, including pattern of reaction, temporal relationship, de-challenge or re-challenge, confounding factors such as concomitant medication, concomitant diseases and relevant history.

Possibly related: There is a reasonable possibility of a causal relationship between the investigational intervention and the AE/SAE. The assessment of causality will be made against the reference safety information (e.g. as found within the Investigator's Brochure or SPC).

 EPAD - 115736	D2.11 Master Statistical Analysis Plan for the EPAD Platform Proof-of-Concept Trial		
	WP2. Statistical/Methodology Engine Room	Version: v2.0 – Final	
	Author(s): [name], [name], [name]	Security: PU	30/36

Unrelated: There is no reasonable possibility of a causal relationship between the investigational intervention and the AE/SAE.

Arguments that may suggest that there is a reasonable possibility of a causal relationship could be:

- The event is consistent with the known pharmacology of an intervention.
- The event is known to be caused by or attributed to the intervention class.
- A plausible time to onset of the event relative to the timing of the intervention.
- Evidence that the event is reproducible when the intervention is re-introduced.
- No medically sound alternative aetiologies that could explain the event (eg, pre-existing or concomitant diseases, or co-medications).
- The event is typically drug-related and infrequent in the general population not exposed to drugs (eg, Stevens-Johnson syndrome).
- An indication of dose-response (ie, greater effect size if the dose or intensity of the intervention is increased, smaller effect size if dose or intensity is diminished).

Arguments that may suggest that there is no reasonable possibility of a causal relationship could be:

- No plausible time to onset of the event relative to the timing of the intervention is evident (eg, pre-treatment cases, diagnosis of cancer or chronic disease within days/weeks of drug administration; an allergic reaction weeks after discontinuation of the intervention concerned)
- Continuation of the event despite the withdrawal of the medication, taking into account the pharmacological properties of the compound (eg, after 5 half-lives). Of note, this criterion may not be applicable to events whose time course is prolonged despite removing the original trigger.

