Appendix I gives example SAS code to fit a simplified version of the primary analysis.

21. Changes to analyses specified in the protocol

There are no changes to analyses specified in the protocol.

22. Details on data handling

Details on data handling will be specified in the ISA.

23. Transfer of data from LCS

Transfer of data from LCS has two purposes. One is avoiding screening assessments, when a similar assessment has been done shortly before. The other point is that the primary endpoint analysis includes data from the LCS as reflection of the status and development of the research participant during their time in the LCS.

At the screening visit (V1), some assessments performed in the LCS within the past 3 to 12 months prior to the screening visit of the PoC trial will be considered acceptable and will not be necessarily re-assessed:

- If the PoC screening visit is performed the same day or within (\leq) 3 months of a LCS visit, then the clinical outcome assessments that are the same in both studies will be performed only once
- If the PoC screening visit is performed more than ($>$) 3 months after a LCS visit, then the clinical outcome assessments will need to be re-performed.

At screening Visit 2, in order to reduce invasive assessments, repetition of examinations and subject burden, the following existing data performed in the LCS within pre-defined time intervals may be eligible:

- Secondary and exploratory clinical outcome assessments within the past 3 months prior to V1
- Lumbar puncture for CSF sampling done in the LCS within past 12 months prior to V1
- MRI performed in the LCS within past 6 months prior to V1.

24. Communication of results

Sharing of placebo data will be conducted between each study cohort. Research participants, Investigators and everyone involved in the conduct or analysis or with any other interest in this trial conduct will not be blinded across different intervention cohorts but will remain blinded with regard

 EPAD - 115736	D2.11 Master Statistical Analysis Plan for the EPAD Platform Proof-of-Concept Trial		
	WP2. Statistical/Methodology Engine Room	Version: v2.0 – Final	
	Author(s): [name], [name], [name]	Security: PU	33/36

to the randomized treatment arm assignments within their intervention cohort until after database lock.

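### Related-event tables pool placebo participants whose events were judged against another trial's drug, so the comparison can be biased in either direction

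*Combined protocol and SAP*

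**What the plan says.** Section 8 sets the default for safety: "Safety analyses are done on the set ASTS-concurrent controls". Section 8.2 defines the concurrent-controls level as "All subjects in all treatment arms in the IST supplemented with control subjects from other ISTs, defined as follows". The borrowed participants are placebo participants in the same strata whose baseline visit falls within the focus IST's enrolment window.

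Section 15 then states that "Frequency, severity, and causal relationship of AEs will be tabulated by system organ class and preferred term". Section 7.5.7 lists adverse reactions among the safety endpoints, and Section 15.1 defines them by at least a reasonable possibility of causality.

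Under Section 15.1 the principal investigator makes the causality judgment, against reference safety information such as an Investigator's Brochure. An event is possibly related when "There is a reasonable possibility of a causal relationship between the investigational intervention and the AE/SAE". Several of the listed supporting arguments are specific to the product, the first being that "The event is consistent with the known pharmacology of an intervention".

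On blinding, Section 5 says "Research participants will not be blinded to which intervention specific trial they participate in". Section 24 says that participants, investigators and others involved "will not be blinded across different intervention cohorts", while they stay blinded to arm within a cohort until database lock.

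**The concern.** Within one IST, active and own-placebo events are rated by the same people, blind to arm, against the same drug. That is what makes a related-event comparison interpretable. A borrowed placebo participant's event was rated by an investigator who knew the participant was in a different IST and who asked whether a different product could have caused it. Once the two are pooled, possibly related has one meaning in the active column and several in the placebo column.

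Matching follow-up time, adjusting for exposure or adding participants does not repair this, because the rating itself refers to another product. Safety is descriptive and no hypothesis test is planned, so the reader judges drug-relatedness directly from these columns. An unremarkable drug could appear to cause reactions, or a real reaction could be masked.

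**Working it through.** **Does the SAP contain a safeguard?** Four places could supply one.

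- Section 14, item 4, checks poolability of controls, but only through RBANS progression (the CPRR).
- Section 24 discusses shared adverse-event data only as a risk of indirect unblinding.
- Section 8 lets an ISA-SAP restrict the analysis sets further but does not require it to do so for causality.
- Section 15 gives no re-adjudication of borrowed events, no own-placebo rule and no caveat.

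The mixture is therefore the default.

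**Size and direction.** The SAP states no adverse-event rate, attribution rate, number of ISTs or safety sample size, so there is no figure of its own to reproduce. The following inputs are assumptions:

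- an event rate p = 10% in every arm, that is, no true drug effect;
- K = 2, 3 or 4 concurrent ISTs of equal size, with full calendar overlap and the same strata;
- a = share of events called related under the focus drug's reference information;
- b = the same share under the other ISTs' drugs.

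The borrowed share of the placebo column is (K−1)/K, which is 50%, 67% and 75% for K = 2, 3 and 4.

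Active related rate = p·a. Pooled placebo related rate = p·[a + (K−1)·b]/K. Apparent ratio = K·a/[a + (K−1)·b]; p cancels.

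| a | b | Active | Pooled placebo, K = 2 / 3 / 4 | Apparent ratio, K = 2 / 3 / 4 |
|---|---|---|---|---|
| 0.6 | 0.2 | 6.0% | 4.0% / 3.3% / 3.0% | 1.50 / 1.80 / 2.00 |
| 0.5 | 0.3 | 5.0% | 4.0% / 3.7% / 3.5% | 1.25 / 1.36 / 1.43 |
| 0.3 | 0.3 | 3.0% | 3.0% / 3.0% / 3.0% | 1.00 / 1.00 / 1.00 |
| 0.2 | 0.4 | 2.0% | 3.0% / 3.3% / 3.5% | 0.67 / 0.60 / 0.57 |
| 0.1 | 0.4 | 1.0% | 2.5% / 3.0% / 3.25% | 0.40 / 0.33 / 0.31 |

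For example, with a = 0.6, b = 0.2 and K = 3: 3 × 0.6/(0.6 + 2 × 0.2) = 1.8/1.0 = 1.80. With a = 0.1, b = 0.4 and K = 4: 4 × 0.1/(0.1 + 3 × 0.4) = 0.4/1.3 = 0.31.

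For unequal ISTs or partial overlap, let w be the borrowed share. The ratio is then a/[(1−w)·a + w·b], which moves towards 1 as w falls.

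**With own placebo only**, both columns carry the share a, so the ratio is p·a/(p·a) = 1.00 whatever a is. **All-causality tables** compare p with p (10% versus 10%) and are untouched.

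**The case against.** Most of the case on the other side concerns how far the point reaches.

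- *Direction.* A reader might infer that these tables will show a false excess for the drug. The documents do not support that. An excess is expected for events in the focus drug's known profile but not in the others'; the reverse pattern gives a deficit; equal shares give no bias. This limit stands.
- *Size.* The borrowed shares of 50% to 75% assume equal ISTs, complete overlap and identical strata. Section 8.2 restricts borrowing by strata and baseline date, so real shares may be smaller. Some causality arguments in Section 15.1, such as alternative aetiology or an event that resolves while treatment continues, do not depend on a drug's known profile and would narrow the gap between a and b. This stands, and it is why the figures are illustrations only.
- *Consequence.* Reporting concentrates on treatment-emergent events, which are defined mainly by timing. The graduation and futility rules in Section 18.1 use only the CPRR. Related-event tables decide nothing formally. This stands too, but with no test planned, the descriptive columns are the safety comparison and need to be comparable.
- *Delegation.* An ISA-SAP may narrow the sets, and under Section 2 the ISA prevails in a conflict. That opens a route to a remedy but does not require one.
- *Unfinished document.* The SAP says it has unfinished parts and flags several. Section 15 is not among those flagged, and the stated purpose is future use, so the default would be inherited.

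A reader might also infer that SAE status is defined differently across ISTs, because Section 7.5.2 leaves seriousness to the ISA when required. That sentence sits under vital signs and may cover only abnormal findings there, while Section 15.1 gives one SAE definition. The documents support no more than an ambiguity, separate from causality.

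**Conclusion.** The point holds for tables that use the causality rating: related adverse events, related serious adverse events and adverse reactions. Followed as written, the plan mixes attribution standards inside the placebo column, and nothing in the SAP corrects or discloses this. The own-placebo part of that column is sound; only the borrowed part is not comparable.

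The bias can run either way. The table's range, from 0.31 to 2.00 with no true effect, rests on assumed attribution shares and on equal, fully overlapping ISTs in the same strata; it is not a forecast. Event frequency regardless of causality is not biased by this mechanism, and no efficacy decision is affected. It should be corrected before the master SAP is reused.

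**What to change.** In Sections 8 and 15:

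1. Base every table of causal relationship, including related SAEs and adverse reactions, on ASTS-IST controls: active versus the IST's own blinded placebo. The naming scheme in Section 8 already provides this set.
2. If borrowed placebo is shown in those tables, give it a separate column, labelled as rated against other interventions and not pooled with own placebo.
3. Keep ASTS-concurrent controls for adverse events regardless of causality.

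Separately, reconcile the seriousness sentence in Section 7.5.2 with the SAE definition in Section 15.1.

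The change needs SAP wording and table shells only, with no new data. The real cost is precision. At 3:1 allocation own placebo is one third the size of the active group, and under the equal-IST assumption the causality comparison gives up 50% to 75% of the pooled placebo column for K = 2 to 4. That matters for infrequent events. The separate column keeps the borrowed data visible, and the all-causality tables keep the full pooled comparator.

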15.1. Definitions of adverse events

Adverse event (AE)

An adverse event is defined as any untoward medical occurrence in a clinical investigation research participant administered an intervention and which does not necessarily have a causal relationship with this intervention.

An AE can therefore be any unfavourable and unintended sign (including an abnormal laboratory finding), symptom, or disease temporally associated with the use of an intervention, whether or not considered related to the intervention.

 EPAD - 115736	D2.11 Master Statistical Analysis Plan for the EPAD Platform Proof-of-Concept Trial		
	WP2. Statistical/Methodology Engine Room	Version: v2.0 – Final	
	Author(s): [name], [name], [name]	Security: PU	29/36

Adverse Reaction (AR)

An AR is defined as a response to an intervention which is untoward and unintended. Response in this context means that a causal relationship between an intervention and an adverse event is at least a reasonable possibility.

Adverse Events of Special Interest (AESI)

Intervention Specific Appendices may define their AESI, if any, for the intervention and appropriate assessments and monitoring. AESI need to be reported within the same timeframe that applies to SAE.

Serious adverse event (SAE)

A SAE is defined as any AE which:

- results in death of the clinical investigation research participant,
- is life-threatening,
- requires inpatient hospitalisation or prolongation of existing hospitalisation,
- results in persistent or significant disability or incapacity,
- is a congenital anomaly or birth defect,
- any other significant medical event, deemed serious for any other reason when based upon appropriate medical judgment, which may jeopardise the patient and may require medical or surgical intervention to prevent one of the other outcomes listed in the above definitions.

Intensity (Severity) of AEs and SAEs

The intensity (severity) of the AE/SAE will be assessed by the PI and should be judged based on the following:

Mild: Awareness of sign(s) or symptom(s) that is/are easily tolerated, causing minimal discomfort and not interfering with usual activities

Moderate: Enough discomfort to cause interference with usual activity

Severe: Incapacitating or causing inability to work or to perform usual activities

Causal relationship of AEs and SAEs

Medical judgment by the PI should be used to determine any causal relationship to the AE/SAE, considering all relevant factors, including pattern of reaction, temporal relationship, de-challenge or re-challenge, confounding factors such as concomitant medication, concomitant diseases and relevant history.

Possibly related: There is a reasonable possibility of a causal relationship between the investigational intervention and the AE/SAE. The assessment of causality will be made against the reference safety information (e.g. as found within the Investigator's Brochure or SPC).

 EPAD - 115736	D2.11 Master Statistical Analysis Plan for the EPAD Platform Proof-of-Concept Trial		
	WP2. Statistical/Methodology Engine Room	Version: v2.0 – Final	
	Author(s): [name], [name], [name]	Security: PU	30/36

Unrelated: There is no reasonable possibility of a causal relationship between the investigational intervention and the AE/SAE.

Arguments that may suggest that there is a reasonable possibility of a causal relationship could be:

- The event is consistent with the known pharmacology of an intervention.
- The event is known to be caused by or attributed to the intervention class.
- A plausible time to onset of the event relative to the timing of the intervention.
- Evidence that the event is reproducible when the intervention is re-introduced.
- No medically sound alternative aetiologies that could explain the event (eg, pre-existing or concomitant diseases, or co-medications).
- The event is typically drug-related and infrequent in the general population not exposed to drugs (eg, Stevens-Johnson syndrome).
- An indication of dose-response (ie, greater effect size if the dose or intensity of the intervention is increased, smaller effect size if dose or intensity is diminished).

Arguments that may suggest that there is no reasonable possibility of a causal relationship could be:

- No plausible time to onset of the event relative to the timing of the intervention is evident (eg, pre-treatment cases, diagnosis of cancer or chronic disease within days/weeks of drug administration; an allergic reaction weeks after discontinuation of the intervention concerned)
- Continuation of the event despite the withdrawal of the medication, taking into account the pharmacological properties of the compound (eg, after 5 half-lives). Of note, this criterion may not be applicable to events whose time course is prolonged despite removing the original trigger.
- Additional arguments amongst those stated before, like alternative explanation (e.g., situations where other drugs or underlying diseases appear to provide a more likely explanation for the observed event than the drug concerned).
 - Disappearance of the event even though the intervention continues or remains unchanged.

16. Pharmacokinetic/Pharmacodynamic analyses

No PK assessments are required in the Master Protocol. If any specific assessments are required for an intervention, they will be articulated in the Intervention Specific Appendix of the Master Protocol and relevant statistical analyses will be described in the ISA of the master SAP.

17. Data monitoring committees

An IDMC, and a separate Data Safety Monitoring Board (DSMB), both independent of the Sponsor and the Intervention Owners, will be established to assess the progress of the clinical trial, including unblinded safety (DSMB) and efficacy (IDMC) assessment at specified intervals, and to recommend to the PSC and ASC whether to continue, modify, or stop interventions within the trial. Measures are in

 EPAD - 115736	D2.11 Master Statistical Analysis Plan for the EPAD Platform Proof-of-Concept Trial		
	WP2. Statistical/Methodology Engine Room	Version: v2.0 – Final	
	Author(s): [name], [name], [name]	Security: PU	31/36

place to ensure confidentiality and blinding of the Sponsor and all other trial participants. The tasks and responsibilities of the IDMC and DSMB will be specified in IDMC and DSMB Charters, respectively. The IDMC and DSMB will maintain written records of all their meetings.

18. Interim analyses

